1.3. Schedule of Activities (SoA)

Table 1: Study Activities for Duvelisib Monotherapy (Cycle 1: 10 Weeks; Cycles ≥2: 4 Weeks)

Activity	Screening D-30 to D-1	Cycle 1					Cycle 2		Cycle 3+	EoT ^a	Safety F/U ^b 30d (+7) postdose		Notes
		D1	D14 (-3)	D29 (+3)	D43 (±3)	D57 (±3)	D1 (±3)	D14 (-3)					
Informed Consent	X												Potentially eligible subjects must sign an ICF prior to initiating any study specific procedures. Standard of care assessments that fulfill study eligibility requirements may be performed prior to subject signing the ICF.
Inclusion/Exclusion Criteria	X												
Randomization	X (D -7 to -1)												Subject must sign informed consent, meet inclusion/exclusion criteria, and complete all other screening activities prior to randomization.
Medical History, Demographics	X												Medical History includes histologic lymphoma diagnostic and prior treatment and response information, FLIPI-1 score
Archival Tumor Tissue	X												Tumor tissue is not required for enrollment, but should be submitted from all enrolled subjects, if available. Sample should be FFPE tissue and will be used to evaluate prognostic biomarkers.
Tumor Biopsy (optional)	X												If a transformation to a more aggressive subtype of lymphoma is suspected, a biopsy may be performed at Investigator's discretion. If this sample is collected, please see Archival Tumor Tissue instructions above.
Full Physical Examination	X	X											If performed within 7 days of C1D1, then screening results can be used for C1D1.
Focused Physical Examination			X	X	X	X	X	X	X	X			Disease-focused assessments including liver/spleen size, clinical assessment of tumor masses, and B symptoms.
Vital Signs	X	X	X	X	X	X	X	X	X	X			Vital signs measured in a semi-supine position after 5 minutes rest.
Computed Tomography (CT)	X									X			All subjects require CT or FDG-PET-CT scans. MRI may be used instead of CT scans if CT cannot

Activity	Screening D-30 to D-1	Cycle 1					Cycle 2		Cycle 3+	EoT ^a	Safety F/U ^b 30d (+7) postdose		Notes		
		D1	D14 (-3)	D29 (+3)	D43 (±3)	D57 (±3)	D1 (±3)	D14 (-3)	D1 (±3)						
Scans of the Chest, Abdomen and Pelvis		Day 1 of Cycles 2, 4, 6, 9, 13, 17, and Every 4th Cycle Thereafter (Window: Day -7 to Day 1 of Each Cycle)											be done, but the same method must be used throughout the study. A scan will be performed at the EoT if one was not performed within 30 days of the EoT Visit.		

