**Figure 1: Treatment Scheme**

Solid sections: duvelisib 25 mg BID; hashed sections: drug holiday. Subjects will be randomized 1:1 to Arms 1 and 2. Subjects will be assessed for disease response on Day 1 of Cycles 2, 4, 6, 9, 13, 17 and every fourth cycle thereafter until disease progression, unacceptable toxicity or withdrawal.

Abbreviations: BID: twice daily.

The study has a 2-stage design. For each arm: in the first stage, 15 subjects will be enrolled. Responses will be assessed by the Investigator according to the 2007 revised IWG criteria (Cheson 2007) (primary endpoint) and the 2014 Lugano criteria (Cheson 2014). The evaluation of the first stage will take place after the enrolled subjects have been followed for a minimum of 3 cycles. If there are fewer than 6 responders (partial response (PR) or complete response (CR)) among the first 15 subjects per arm, consideration may be given to stopping that arm. A treatment arm may also not proceed to the second stage if the totality of the data is compelling (e.g., accumulating enough data in Stage 1 to conclude the overall response rate (ORR) exceeds 30%). Otherwise, approximately 36 additional subjects will be enrolled for a total of 51 per arm. Enrollment will be continuous between Stage 1 and Stage 2. If fewer than 22 (43%) responders (PR or CR) are observed in 51 subjects, consideration may be given to concluding that the treatment schedule does not warrant further study in this population. Each arm will be evaluated separately.

It is anticipated that study enrollment will occur over approximately 2 years. The last subject visit will occur 2 years after the last subject is randomized. If the study ends prior to all subjects discontinuing treatment, any subject continuing to receive benefit will be provided the opportunity to continue to receive duvelisib. Long-term continued treatment may be provided via an expanded access program consistent with local regulations, such as the Secura Bio NPP. Study procedures and their timing are summarized in the schedule of assessments (SoA) (Protocol Section 1.3).

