#### 4.10.3 Secondary Efficacy Variables

The secondary efficacy analyses will be conducted on the mITT analysis set.

- ORR according to 2014 Lugano criteria (Cheson 2014) will be analyzed in the same fashion as the primary endpoint

*Note: with the exception of TTF, all additional secondary response endpoints (described below) as well as PFS will be assessed separately using 2007 revised IWG criteria (Cheson 2007) and 2014 Lugano criteria (Cheson 2014)*

- ORR, at 6, 12, 18, and 24 months after first dose of study intervention, defined as the proportion of subjects achieving CR or PR at each of these time points.
- PFS will be assessed using KM methods from time of first dose of study intervention to PD or death. Median PFS will be estimated, along with the 95% CI. The 6-month and 12-month PFS estimates will also be presented. See Table 1 for event and censoring definitions. Kaplan-Meier survival curves by arm will be produced.
- TTF will be calculated as the time from first dose of study intervention until discontinuation for any reason and will be summarized using KM methods. Median TTF will be estimated, along with the 95% CI. The 6-month and 12-month TTF estimates will also be presented. Subjects who are still on treatment at time of data cutoff will be censored at their last dose date. Kaplan-Meier survival curves by arm will be produced.
- DOR will be calculated for those subjects with a CR or PR from the time of first response to PD using KM methods. Median DOR will be estimated, along with the 95% CI. The 6-month and 12-month DOR estimates will also be presented. See Table 1 for event and censoring definitions. Kaplan-Meier survival curves by arm will be produced.
- OS will be assessed using KM methods from time of first dose of study intervention to death. Median OS will be estimated, along with the 95% CI. The 6-month and 12-month OS estimates will also be presented. Subjects without documented death will be censored at their last known alive date. Kaplan-Meier survival curves by arm will be produced.
- LNRR will be calculated as the proportion of subjects achieving  $\geq 50\%$  decrease in the sum of the product of the diameters of target lymph nodes. A 2-sided 95% exact CI for LNRR will also be estimated. A waterfall plot of minimum percent change in the sum of the product of the diameters by arm will be produced.

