**Table 1: Primary PFS Censoring/Event Rule**

Situation	Date of Event or Censoring	Outcome
No adequate baseline disease status assessment	Date of randomization + 1 day	Censored

No adequate post-baseline disease status assessment unless death occurs prior to first scheduled post-baseline assessment	Date of randomization + 1 day	Censored
No documented progression or death	Date of last adequate disease status assessment	Censored
Documented progression with $\leq 1$ missing scheduled disease status assessment before progression	Date of the earliest assessment that results in a finding of unequivocal progression	Event
Death before progression being documented with $\leq 1$ missing scheduled disease status assessment before death	Date of death	Event
Documented progression or death following a gap between adequate disease status assessments equivalent to 2 missed visits	Date of last adequate disease status assessment before the gap	Censored
New anticancer treatment or procedure started before documented progression	Date of last adequate disease status assessment prior to start of new anticancer therapy	Censored

Note: Disease status assessment includes radiologic documentation (CT, PET/CT, MRI scans) (chest, abdomen and pelvis, others as clinically indicated), bone marrow biopsy/aspirate (may not be required of all patients at all scheduled disease status assessments), and focused physical examination (disease related symptoms, liver and spleen assessment). An adequate baseline disease assessment is any assessment with measurable target lesions from scans. An adequate post-baseline disease status assessment is any disease status assessment for which a disease status of CR, PR, SD or PD is arrived per revised International Working Group (IWG) response criteria for malignant lymphoma.

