### 4.13 Determination of Sample Size

The sample size for each arm was calculated using a 2-stage approach.

For each arm: in Stage 1, 15 subjects will be randomized. The evaluation of the first stage will take place after the 15 enrolled subjects have been followed for a minimum of 3 cycles (18 weeks).

If there are fewer than 6 responders (PR or CR) among the first 15 subjects, consideration may be given to terminate the treatment arm. The decision to proceed to Stage 2 will be based on the totality of data observed, including types of responses, safety data, and discontinuation rates. The treatment arm may also not proceed to Stage 2 if the totality of the data is viewed as compelling;

such scenarios could include (but are not limited to) accumulating enough data in Stage 1 to conclude the ORR exceeds 30%. If the treatment arm proceeds to Stage 2, up to 36 additional subjects will be enrolled for a total of 51. If fewer than 22 (43%) responders (PR or CR) are observed in 51 subjects, consideration may be given to conclude that the treatment schedule does not warrant further study in this population. The final evaluation of each schedule will be based on the totality of data observed, including types of responses, safety data, and discontinuation rates. This design yields a type I error rate of 0.025 (1-sided) and power of 90% under the assumptions described above.

Subjects will be stratified by number of prior therapies (1 or  $> 1$ ), bulky disease status (longest diameter of baseline lesion  $< 5$  cm or  $\geq 5$  cm) and time since last recurrence ( $\geq 24$  months or  $< 24$  months).

Note: "Enrolled" means subjects', or their legally acceptable representative's, agreement to participate in a clinical study following completion of the informed consent process. Potential subjects who are pre-screened for the purpose of determining eligibility for the study but do not sign an informed consent form (ICF) are not considered enrolled.

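### SAP Table 1 gives two outcomes, censored at the start or PFS event, for a subject with no adequate post-baseline assessment who dies between the first and second scheduled scans

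*SAP*

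**What the plan says.** SAP 4.10.3 gives the endpoint: "PFS will be assessed using KM methods from time of first dose of study intervention to PD or death". The same bullet refers to Table 1 for event and censoring definitions. The rows of Table 1 are not numbered; counting from the top, three matter here.

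- **Row 2** applies to "No adequate post-baseline disease status assessment unless death occurs prior to first scheduled post-baseline assessment". Outcome: censored. Date: "Date of randomization + 1 day".
- **Row 5** applies to death before documented progression with at most one "missing scheduled disease status assessment before death". Outcome: event on the date of death. The row does not require an earlier adequate post-baseline assessment.
- **Row 6** applies to "Documented progression or death following a gap between adequate disease status assessments equivalent to 2 missed visits". Outcome: censored at the last adequate assessment before the gap.

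The note under the table calls a post-baseline assessment adequate only if it yields CR, PR, SD or PD. Neither the table, its note nor Section 4.10.3 says which row prevails when two apply.

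The schedule is in the SAP Figure 1 legend: "Subjects will be assessed for disease response on Day 1 of Cycles 2, 4, 6, 9, 13, 17 and every fourth cycle thereafter". Protocol Table 1 gives a 10-week first cycle and 4-week cycles after that.

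**The concern.** For one narrow group of deaths, rows 2 and 5 both apply and give opposite outcomes. Two programmers working from the SAP could code the same death differently, and in an open-label trial the choice would be made with the arm known. Under row 2 the subject contributes neither an event nor time at risk. That censoring is informative, because these subjects are removed although they are known to have died, and it can only raise the PFS estimate. The SAP plans no PFS sensitivity analysis that would expose the difference.

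**Working it through.** **Timing.** Inputs: cycle lengths from Protocol Table 1; scan schedule from the SAP Figure 1 legend.

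- Three cycles = 10 + 4 + 4 = 18 weeks, which reproduces the figure in SAP 4.13.
- First scheduled scan, C2D1: 10 × 7 + 1 = day 71.
- Second scheduled scan, C4D1: 18 × 7 + 1 = day 127.
- Interval between them: 127 − 71 = 56 days, or 8 weeks. The 7-day scan windows (days 64–71 and 120–127) make the edges approximate.

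**Which rows apply to a death with no adequate post-baseline assessment.**

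| Death | Scheduled scans missed | Row 2 | Row 5 | Row 6 |
|---|---|---|---|---|
| Before about day 71 | 0 | exempt | event | – |
| About day 71 to 127 | 1 | censored | event | – |
| After about day 127 | 2 or more | censored | does not apply | censored |

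Only the middle line has contradictory outcomes. In the last line the two censoring dates differ (row 6 goes back to baseline), but the outcome does not.

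**Example.** A subject stops in week 9 (days 57–63), has no evaluable scan and dies in week 12 (days 78–84). One Day 1 scan is missing. Row 2 censors and row 5 counts an event. Even with a last dose on day 57, the 30-day reporting period in Protocol 8.3.3 runs to day 57 + 30 = 87, so the death would be captured.

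**Where row 2 puts the subject.** Protocol Table 1 places randomization on Day −7 to −1. Randomization plus one day therefore falls between six days before the first dose and the day of the first dose. Measured from first dose, the censoring time is zero or negative, so the subject is in no risk set.

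**Size per death.** Take an arm of 51 with one affected death, no other early censoring, and PFS p at 6 months in the other 50 subjects. The affected death falls before 6 months.

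- Row 2: estimate = p.
- Row 5: estimate = 50p/51.
- Difference: p − 50p/51 = p/51.
- p = 0.75: 0.75/51 = 0.0147, or 1.5 points.
- p = 0.90: 0.90/51 = 0.0176, or 1.8 points.

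**More than one death.** With k affected deaths the row 5 estimate is (51 − k)/51 times the row 2 estimate. The documents give neither k nor a PFS distribution, so the following is illustrative. It assumes deaths at week 12 and exponential PFS with a 12-month median in the other subjects.

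| k | Factor | 6-month PFS, row 2 | 6-month PFS, row 5 |
|---|---|---|---|
| 1 | 0.980 | 0.700 | 0.686 |
| 3 | 0.941 | 0.708 | 0.667 |
| 5 | 0.902 | 0.717 | 0.647 |

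With k = 3, an assumed median of 9 months gives 0.625 against 0.588, and 18 months gives 0.792 against 0.745.

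**The case against.** **Row 2 is the specific rule and governs.** This is a natural reading: row 2 is written for subjects with no post-baseline assessment and carries its own exception for death. It would settle the ambiguity, but not well. A death just before C2D1 would be an event and one two weeks later would not. It also departs from the table's own tolerance of one missed assessment: a subject who has the C2D1 scan, misses C4D1 and dies before C6D1 is an event, while one who misses only C2D1 and dies before C4D1 is dropped.

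**Censoring a death is not in itself against the SAP.** A reader might infer that row 2 contradicts the PFS definition. The documents do not support that, because the PFS bullet hands event and censoring rules to Table 1, and row 6 openly censors some deaths. The fault is the clash between rows.

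**What counts as scheduled is undefined after discontinuation.** Protocol Table 1 asks for an end-of-treatment scan if none was done within 30 days. If that scan counts as scheduled and was also missed, two are missing and row 5 no longer applies. The SAP's own list of assessment days contains only the Day 1 scans, which supports counting one, but the SAP does not say so. This stands, and the fix has to cover it.

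**Few subjects will qualify.** This also stands. The subject needs no evaluable end-of-treatment or C2D1 scan, no new anticancer therapy, and a recorded death in an 8-week interval. Capture is uncertain after early stopping. A last dose in week 6 (day 42 at the latest) closes the reporting period by day 42 + 30 = 72, before a death in week 13 (from day 85). Protocol 6.7 still mentions survival follow-up, but the schedule shows no visit after the 30-day safety follow-up.

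**The effect is small beside sampling error.** With 51 subjects the binomial standard error is √(0.75 × 0.25/51) = 6.1 points at p = 75% and √(0.90 × 0.10/51) = 4.2 points at p = 90%. One death moves the estimate by about 0.24 and 0.42 of a standard error. This is true, but the error goes in one direction and is avoidable.

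**Conclusion.** The conflict is real and confined to deaths between about day 71 and day 127 in subjects with no adequate post-baseline assessment and only one missed scheduled scan. Applying row 2 overstates that arm's PFS by about p/51 per death, given 51 subjects and no other early censoring. The number of such deaths is not given and is probably small.

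Two wider conclusions are tempting and not supported. One is that every death after the first scan was due has two rules; from the second missed scan on, rows 2 and 6 both censor. The other is that these failures disappear from the trial. The subject remains a non-responder in the mITT denominator for ORR, a TTF event at discontinuation and, if the death is known, an OS event. DOR is untouched, since responders have an adequate assessment. PFS is not tested and enters no numerical stage rule. The point is worth correcting because an event rule with two answers cannot be programmed reproducibly.

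**What to change.** In SAP Table 1:

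1. Extend the row 2 exception to any death before the second scheduled post-baseline assessment (C4D1).
2. State that such deaths are PFS events on the date of death under row 5.
3. Define scheduled assessments as the Day 1 scans of Cycles 2, 4, 6 and so on, by calendar time from first dose, whether or not the subject is still on treatment. State that the end-of-treatment scan does not count as a missed scheduled assessment.
4. Apply the same rule to PFS under both the revised IWG and the Lugano criteria.

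Cost: a changed phrase and two clarifying sentences. No new data collection is needed, although the rule can only act on deaths that are recorded. The downside is that PFS may look slightly less favourable.

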## 4.11 Safety Evaluation

All safety summaries and analyses will be based upon the AT Analysis Set as defined in [Section 4.5](#).

### 4.11.1 Extent of Exposure

Extent of exposure will be summarized for each treatment arm based on the AT analysis set. Extent of exposure will be summarized for the following variables:

- Duration (months): (date of last dose – date of first dose + 1) divided by (365.25/12).
- Number of cycles started (continuous and categorical)
- Relative dose intensity (overall and by cycle), defined as  $100\% \times (\text{total dose received})/(\text{planned cumulative dose for the duration of treatment})$ . The planned cumulative dose for the treatment duration is defined as 25 mg BID  $\times$  total number of days on which duvelisib is scheduled to be administered during the interval between first dose date and last dose date. The treatment scheme is provided in [Section 3.1](#).
- Number and percentage of subjects with a dose reduction
- Time from first dose to first dose reduction

- Total days spent at dose reduction: last date of dose reduction – first date of dose reduction + 1
- Number and percentage of subjects with an unplanned dose hold (excluding the planned 2-week holidays for each arm)
- Number and percentage of subjects with an unplanned dose hold < 7 days,  $\geq$  7 days
- Time from first dose to first unplanned dose reduction
- Number and percentage of subjects for whom study drug was discontinued

A by-subject listing will be presented for exposure to study drug

#### 4.11.2 Adverse Events

Adverse events will be coded using Medical Dictionary for Regulatory Activities (MedDRA) Version 22 or higher. The severity grade of the AE will be assessed by the Investigator according to the National Cancer Institute Common Terminology Criteria for Adverse Events (NCI-CTCAE, Version 5.0). If an AE is not included in the NCI-CTCAE Version 5.0, the severity grade of the AE will be assessed by the Investigator according to the study protocol.

A treatment-emergent adverse event (TEAE) is defined as any AE that emerges or worsens in the period from the first dose of duvelisib to 30 days after the last dose of duvelisib. The onset date of an AE will be compared to the first dose date and the last dose date plus 30 days (inclusive) to determine whether the AE is treatment-emergent or not. Refer to [Section 4.3.1.2](#) for the algorithm to determine whether an AE is treatment emergent if the onset date of an AE is completely or partially missing.

TEAEs will be summarized for each treatment arm by MedDRA SOC and PT, or PT only, or SOC only. For summary tables by SOC and PT, SOC will be sorted alphabetically, and PT will be sorted by decreasing frequency in Arm 1 within each SOC. For summary tables by PT only, PT will be sorted by decreasing frequency. For selected summaries (indicated in the list below), TEAEs will be summarized by SOC, high-level group term (HLGT) and PT, sorted by most frequently occurring SOC.

If multiple TEAEs of the same PT are reported for a subject, only the maximum grade observed for this PT will be included in summary of TEAEs by grade; the subject will be counted only once in the number of subjects for this PT and only once for the number of subjects for the SOC to which the PT is classified.

An overview TEAE summary table will be provided which will include the number of subjects with AEs in selected categories. In addition, TEAEs will be summarized for the following categories, and will be tabulated by SOC and PT, unless otherwise specified.

- TEAEs (all grades, all causalities)
- Treatment-related TEAEs (all grades)
- TEAEs by maximum grade (all causalities)

- Treatment-related TEAEs by maximum grade
- Grade 3 or higher TEAEs (all causalities)
- Grade 3 or higher treatment-related TEAEs
- Treatment-emergent SAEs (all causalities)
- TEAEs resulting in discontinuation of study drug (all causalities)
- TEAEs resulting in dose hold (all causalities)
- TEAEs resulting in dose reduction (all causalities)
- TEAEs resulting in dose hold or reduction (all causalities)
- TEAEs resulting in any dose modification (dose hold, dose reduction and/or discontinuation)
- TEAEs occurring during the first 10 weeks of treatment
- Treatment-related TEAEs resulting in discontinuation of study drug
- TEAEs by resolution status (resolved/resolved with sequelae vs. not resolved)
- Grade 3 and or higher TEAEs by resolution status (resolved/resolved with sequelae vs. not resolved)
- Treatment-emergent SAEs by resolution status (resolved/resolved with sequelae vs. not resolved)
- TEAEs resulting in death (all causalities)
- Treatment-related TEAEs resulting in death
- TEAEs reported in  $\geq 20\%$  of all treated subjects by PT (all grades, all causalities)
- Grade 3 or higher treatment-emergent AEs reported in  $\geq 20\%$  of all treated subjects by PT (all causalities)
- Treatment-emergent SAEs reported in  $\geq 2\%$  of all treated subjects by PT (all causalities)
- TEAEs reported in  $\geq 5\%$  of subjects and occurred at  $\geq 2\%$  higher incidence in subjects on Arm 1 (all grades, all causalities)
- Grade 3 or higher TEAEs reported in  $\geq 5\%$  of subjects on either arm (all causalities)

A by-subject listing of the following AE categories will be presented.

- All AEs (TEAEs will be flagged)
- All SAEs (TEAEs will be flagged)
- All SAE reported with the term disease progression
- TEAEs resulting in dose hold
- TEAEs resulting in dose reduction
- TEAEs resulting in discontinuation of study drug
- TEAEs resulting in death (see [Section 4.11.3](#) for full characterization of deaths)
- TEAEs resolved or resolved with sequelae
- TEAEs not resolved

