8.3.2. Definition of a Serious Adverse Event

An SAE is any untoward medical occurrence at any dose (including after the ICF is signed and prior to dosing) that:

- Results in death
- Is life-threatening (subject is at immediate risk of death from the event as it occurred)
- Requires inpatient or prolongation of existing hospitalization
- Results in persistent or significant disability/incapacity
- Results in a congenital anomaly/birth defect

Important medical events that may not result in death, are not immediately life-threatening, or do not require hospitalization may be considered SAEs when, based on appropriate medical judgment, they may jeopardize the subject and may require medical or surgical intervention to prevent one of the outcomes listed in this definition. Examples of such events include allergic bronchospasm requiring intensive treatment in an emergency room or at home, blood dyscrasias or convulsions that do not result in inpatient hospitalization, or the development of drug dependency or drug abuse.

For SAE reporting purposes, hospitalization is defined as inpatient hospital stay. Hospitalizations for elective surgery or other medical procedures that are not related to a TEAE are not considered SAEs. Hospitalization, which in the opinion of the Investigator, is unrelated to the study intervention, and due to purely non-medical circumstances (e.g., respite care, lack of a caretaker at home, lack of transportation home) are also not considered to be SAEs. PD under study (including signs and symptoms of progression) if documented by use of appropriate methods, should not be reported as an SAE unless the outcome of the PD is fatal during the study or within the safety reporting period (see Section 8.3.3, Reporting of Adverse Events and Serious

Adverse Events). If the malignancy has a fatal outcome during the study or within the safety reporting period, then the event should be reported using the term "disease progression" with a Common Terminology Criteria for Adverse Events (CTCAE) severity of Grade 5.

Death should not be reported as an SAE. The primary reason for a subject's death should be reported as an SAE, with death reported as the outcome.

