8.3.3. Reporting of Adverse Events and Serious Adverse Events

The AE reporting period begins from the time that the subject signs the ICF through and including 30 calendar days after the last study intervention dose. All subjects with treatment-related AEs/SAEs should be observed until resolution or stabilization. Any SAE occurring after the reporting period must be promptly reported if a causal relationship to the investigational drug is suspected. If the subject begins a new anticancer therapy, the safety reporting period ends at the time the new treatment is started, however, death must always be reported if it occurs during the AE reporting period irrespective of intervening treatment.

Elective or previously scheduled hospitalizations for pre-existing conditions that have not worsened after initiation of treatment should not be classified as SAEs. For example, an admission for a previously scheduled ventral hernia repair would not be classified as an SAE.

All AEs should be recorded individually unless, in the opinion of the Investigator or designated physician, the AEs constitute components of a recognized condition, disease, or syndrome. In the latter case, the condition, disease, or syndrome should be reported rather than each individual sign or symptom. If a constellation of signs and/or symptoms cannot be medically characterized as a single diagnosis or syndrome at the time of reporting, each individual event should be recorded as an AE or SAE as appropriate on the relevant form(s) (SAE Report Form and/or AE CRF). If a diagnosis is subsequently established, it should be reported as follow-up information becomes available. If a diagnosis is determined after the reporting of the constellation of symptoms, the signs/symptoms should be updated to reflect the diagnosis.

Each AE will be evaluated for duration, severity, seriousness, and causal relationship to the investigational drug. The action taken with study intervention and the outcome must also be recorded.

All SAEs, regardless of relationship to the study intervention, must be reported immediately (within 24 hours of awareness of event by Investigator) to the Sponsor and Contract Research Organization (CRO) pharmacovigilance group. Initial SAE notification should be made by e-mailing or faxing the SAE report form to the e-mail or fax number provided on the SAE report form.

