#### 4.10.2 Primary Efficacy Variable – ORR

The ORR (proportion of subjects achieving a CR or PR using the number of subjects in the mITT analysis set as the denominator) will be estimated, along with the 2-sided 95% exact CI using the Clopper-Pearson exact method for binomial proportions. Responses for the primary ORR analysis will be assessed using the 2007 revised IWG criteria (Cheson 2007). Missing data will be imputed by assuming that any subjects not exhibiting a response (CR or PR) are non-responders. Responses occurring after the start of subsequent anticancer therapy will not be included in the numerator.

The primary analysis of ORR will be performed 12 months after the last subject is randomized, using the time windows specified in [Section 4.2](#) as applicable.

A by-subject listing of the primary efficacy data will be provided.

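### If a subject starts a new anticancer therapy within 30 days of last dose, the SAP still counts TEAEs after the protocol has stopped routine AE reporting, so fatal events can be over-represented in the TEAE tables

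*SAP*

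**What the plan says.** **Collection.** Protocol 8.3.3 runs AE reporting from consent "through and including 30 calendar days after the last study intervention dose". It then shortens this for one group: "If the subject begins a new anticancer therapy, the safety reporting period ends at the time the new treatment is started". Two kinds of event must still be reported after that. The first is deaths: "death must always be reported if it occurs during the AE reporting period irrespective of intervening treatment". The second is drug-related serious events: "Any SAE occurring after the reporting period must be promptly reported if a causal relationship to the investigational drug is suspected". A death enters the AE data as a fatal SAE, because Protocol 8.3.2 states: "The primary reason for a subject's death should be reported as an SAE, with death reported as the outcome".

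**Analysis.** SAP 4.11.2 defines a TEAE as "any AE that emerges or worsens in the period from the first dose of duvelisib to 30 days after the last dose of duvelisib", and the date comparison uses only the first and last dose dates: "The onset date of an AE will be compared to the first dose date and the last dose date plus 30 days (inclusive"). The partial-date rule in SAP 4.3.1.2 and the death tables in SAP 4.11.3 use the same 30-day limit. None of the SAP's safety sections mentions new anticancer therapy.

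**Elsewhere in the SAP.** The start of new therapy is used for efficacy. For ORR, SAP 4.10.2 says: "Responses occurring after the start of subsequent anticancer therapy will not be included in the numerator". Table 1 of the SAP censors PFS at the last adequate assessment before new therapy.

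**The concern.** The rule for collecting events and the rule for counting them part company when a subject switches treatment, and the gap depends on the type of event. From the switch to day 30, deaths from any cause must still be reported, while most non-fatal events need not be. The SAP nevertheless treats the whole interval as duvelisib treatment-emergent time.

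Two things follow. A fatal event that begins after the switch, and may be due to the next regimen, is tabulated as a fatal duvelisib TEAE. Non-fatal events in the same interval appear only if the site happened to go on recording them. Safety and tolerability is a secondary objective, and Protocol 4.2 asks whether the drug holidays reduce the frequency, severity or duration of AEs. Attribution to duvelisib therefore matters, even in descriptive tables.

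**Working it through.** The plan states no figure on this point, so the check sets the two rules side by side.

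**Step 1. Events with onset after the switch and no later than last dose + 30 days.**

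| Event | Must the site report it (Protocol 8.3.3)? | Counted as a TEAE (SAP 4.11.2)? |
|---|---|---|
| Fatal, any cause, death by day 30 | Yes | Yes |
| Non-fatal SAE, suspected related to duvelisib | Yes | Yes |
| Non-fatal SAE, not suspected related | No | Yes, if recorded |
| Non-serious AE, related or not | No | Yes, if recorded |

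The first two rows are complete by rule. The last two depend on the site. A fatal event whose onset came before the switch was collected in the ordinary way and is properly a TEAE under either rule.

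**Step 2. Length of the mismatch.** Let d be the number of days from last dose to the switch. The documents do not give d, so the values below are assumptions.

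Days with unequal ascertainment = 30 − d.

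- d = 1: 29 of 30 days, the longest possible gap for a switch after last dose
- d = 7: 23 of 30 days (77%)
- d = 14: 16 of 30 days (53%)
- d = 21: 9 of 30 days (30%)
- d ≥ 30: no mismatch

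**Step 3. Weight of one event.** Protocol 9.2 plans 51 subjects per arm. If all are dosed, one fatal event with post-switch onset adds 1/51 = 2.0 percentage points to that arm's fatal TEAE rate.

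**Step 4. Is the gap closed elsewhere?** Footnote b to the protocol's Schedule of Activities places the safety follow-up visit 30 (+7) days after last dose and asks, where possible, that it precede subsequent therapy. That is a preference, and it cannot be met at day 30 if the subject has already switched. SAP 4.11.3 splits fatal events at 30 days from last dose and by relationship to duvelisib, but not at the switch. Nothing in SAP 4.3.1.2, 4.11.2 or 4.11.3 resolves the mismatch.

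**The case against.** The strongest reply is that there is no contradiction. Protocol 8.3.3 tells sites what to report, SAP 4.11.2 tells programmers how to classify what was reported, and both can be followed as written. The protocol deliberately keeps deaths to day 30 whatever treatment intervenes, and counting them all is conservative for safety, just as dropping post-switch responses is conservative for efficacy. Post-switch deaths may be due to duvelisib, to lymphoma or to an event that began before the switch. Treatment-related fatal TEAEs have their own table. All AEs and deaths are listed by subject, and subsequent therapies are coded (SAP 4.3.2), so a careful reader could find the events concerned. Protocol 9.4.1 plans no formal testing of safety and no formal comparison between arms.

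Much of this stands. The two rules are compatible as instructions, and the different handling of ORR and PFS is not itself an inconsistency; it shows only that the SAP already needs the switch date. A reader might infer that fatal TEAE rates *are* overstated. The documents do not show this, because nothing in them attributes such deaths to the next regimen.

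What does not stand is the claim that a fixed 30-day window is conservative throughout. It is so only where events are collected to its end. After a switch that holds for deaths and suspected-related SAEs, but not for other non-fatal events. The related-only table and the listings help with interpretation, but they do not mend the all-causality tables.

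**Conclusion.** The mismatch is real and unresolved, and it is minor. It concerns only subjects who start new anticancer therapy within 30 days of last dose. For them, the TEAE tables combine complete capture of fatal events with incomplete capture of non-fatal ones. Fatal TEAE rates can be overstated, and non-fatal counts can vary with site practice.

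The only size that can be given is 2.0 percentage points per fatal event with post-switch onset, assuming all 51 subjects in the arm are dosed. The number of such events is unknown.

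Three stronger readings should be resisted:

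- **That a stated share of each arm is affected.** The documents give no count of early switchers. Even a switcher alters a table only if a relevant event falls in the remaining days.
- **That no non-fatal events are collected after a switch.** SAEs suspected to be related to duvelisib still must be reported.
- **That the laboratory window in SAP 4.11.4 has the same fault.** Protocol 8.3.3 governs AE and SAE reporting. Laboratory follow-up is in Protocol 8.2.4, which uses 30 days after last dose without a cut at new therapy.

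**What to change.** 1. In SAP 4.11.2 and 4.3.1.2, end the treatment-emergent AE window at the earlier of last dose + 30 days and the start of new anticancer therapy. State on which side of the cut an onset on the switch day falls.
2. Retain as TEAEs those SAEs suspected to be related to duvelisib with onset after the switch and up to day 30. This matches what Protocol 8.3.3 requires sites to report. Extending it to non-serious related events would bring back dependence on site practice. State how missing causality is handled here, since SAP 4.11.2.1 treats it as related.
3. In SAP 4.11.3, tabulate deaths after the switch but within 30 days of last dose in a separate row, with their relationship to duvelisib. No death is then lost from view.
4. Flag post-switch AEs in the by-subject listings.
5. Leave the laboratory window in SAP 4.11.4 unchanged.

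The cost is SAP wording, one extra table row and a listing flag. The switch date is already needed for ORR and PFS. No change to data collection or to the protocol is required.
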